14.10. Analyses of Secondary Endpoints

Sensor values from primary sensor will be compared to YSI plasma glucose values during YSI FSTs. And the 95% Confidence Interval of MARD, mean rate in Zone A+B of Clarke Error Grid and Consensus Error Grid will be provided.

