6.8 Adjustments for Multiple Comparisons

No adjustments will be made.

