6.9 Significance Level and Statistical Analysis Software

For the statistical analysis of the primary endpoint and secondary endpoints, the level of significance will be set at one-sided 0.025. The level of significance of tests performed on other indicators will be set at two-sided 0.05 level (except special cases). SAS® 9.4 statistical software and R3.5.2 are applied for statistical analysis.

7. Indicators and Statistical Analysis Methods

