7.7 Secondary Endpoints

For the secondary endpoints including:

- a) a mean rate in Zone A+B of Consensus Error Grid between Enlite Sensor values and YSI plasma glucose values during YSI FST days.
- b) a mean rate in Zone A+B of Clarke Error Grid between Enlite Sensor values and YSI plasma glucose values during YSI FST days.
- c) Mean absolute relative difference (MARD) between Enlite Sensor values and YSI plasma glucose values during YSI FST days.

The analyses of a) and b) based on measurement level will be provided. One sample T test will be used for the analysis of c) mean absolute relative difference (MARD) based on subject level. The 95% confidence limit of a), b) and c) will be calculated and tested against corresponding threshold pre-specified in guideline principles.

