7.9.2 Sensor Calibration

Characteristics of Enlite Sensor calibration will be evaluated by:

- Rate of change (less than (<)-4.0 mg/dL/min, -4.0 to -2.5 mg/dL/min, -2.5 to -2.0 mg/dL/min, -2.0 to -1.5 mg/dL/min, -1.5 to -1.0 mg/dL/min, -1.0 to +1.0 mg/dL/min, +1 to +1.5 mg/dL/min, +1.5 to +2.0 mg/dL/min, +2.0 to +2.5 mg/dL/min, +2.5 to +4.0 mg/dL/min, and greater than (>) +4.0 mg/dL/min).

The detailed calculation is as following:

Rate of change for each SG point can be calculated using the SGs within +/- 20 minutes of that SG point. The rate of change is calculated by the formula below:

For each of SGs before SG of interest:

$$(SG_interest - SG_before(i))/time_interval, i=1, 2, 3, 4, \dots\dots$$

For each of SGs after SG of interest:

$$(SG_after(i) - SG_interest)/time_interval, i=1, 2, 3, 4, \dots\dots$$

Then we average all values to get the rate of change and it can be summarized into different categories.

- Rate of change arrows that are displayed to users.

7.9.3 Clarke Error Grid Analysis (EGA) of Paired Sensor and YSI and Reference Values

1) Description

Clarke EGA separates paired observations into five zones of clinical significance. The presence and severity of possible treatment error based on interstitial glucose assay evaluated by the sensor defines the five zones. Zone A represents the absence of treatment error, where the evaluation method and the reference method are within 20% of one another or in which both methods indicate hypoglycemia. Zone B represents cases where the two methods disagree by more than 20%, but do not lead to treatment error. Zones C, D, and E represent increasingly large and potentially harmful discrepancies between the evaluation and the reference method. If the method under evaluation has a high percentage (greater than (>) 90%) of its pairs in Zones A and B, then it is considered clinically acceptable [Clarke et al, 1987].

2) Statistical analysis

Summary statistics (N, %) for each of the zones, as well as combined Zones A and B, will be calculated.

In order to evaluate differing levels of accuracy at various YSI defined glucose levels, the number and percentage of paired observations falling into Zones A, B, A+B, C, D, and E will be provide form YSI glucose ranges of 40-80 mg/dL, greater than (>) 80-120 mg/dL, greater than (>)120-240 mg/dL, and greater than (>) 240 mg/dL.

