7.13 Changes to Planned Analysis

1. Analysis result of Continuous Error Grid will not be provided in statistical analysis report as there is no requirement in CFDA registration technical review guideline.
2. Evaluation of “First calibration SMBG value ranges (40 - 70 mg/dL, 70 – 180 mg/dL and 180 - 400 mg/dL): the numerical Sensor Glucose Value (SGV) accuracy will be evaluated against YSI stratified by the first calibration SMBG value up to the second calibration SMBG.” will not be provided in the analysis report as there is no requirement in CFDA registration technical review guideline.

8. Validation Requirements

Level I or Level II validation are required for analysis output. Level I requires that the peer reviewer independently programs output and then compares the output with that generated by the original Statistical Programmer. Level II requires that the peer reviewer reviews the code; where appropriate, performs manual calculations or simple programming checks to verify the output.

9. Mock Tables, Listings and Figures

See SAP appendix tables, listings and figures.

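### The SAP turns three secondary endpoints that the protocol only estimates into unadjusted one-sided 0.025 tests, so the family-wise error across the three is not controlled

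*SAP*

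**What the plan says.** **Protocol.** Section 14.10 says of the secondary endpoints: "And the 95% Confidence Interval of MARD, mean rate in Zone A+B of Clarke Error Grid and Consensus Error Grid will be provided". The synopsis and section 5.2.2 say the same. None of them gives a hypothesis, a limit or a test. Section 14.9 defines study success by the primary endpoint only: the lower 97.5% confidence limit of the mean agreement rate must exceed 60%.

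**SAP.** Section 7.7 says of Consensus A+B (a), Clarke A+B (b) and MARD (c): "The 95% confidence limit of a), b) and c) will be calculated and tested against corresponding threshold pre-specified in guideline principles". Section 6.9 sets the level: "For the statistical analysis of the primary endpoint and secondary endpoints, the level of significance will be set at one-sided 0.025". Section 6.8, on multiple comparisons, reads in full: "No adjustments will be made". Section 6.1 states a null and an alternative for the primary endpoint only.

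The unit of analysis differs among the three. For the two zone rates, "The analyses of a) and b) based on measurement level will be provided". For MARD, "One sample T test will be used for the analysis of c) mean absolute relative difference (MARD) based on subject level".

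Section 7.13 lists two changes to the planned analysis, both of them omissions. The move from interval to test is not listed.

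**The concern.** The protocol has one formal decision. The SAP adds three more threshold tests at the same level, with no order among them, no dependence on the primary result and no allowance for there being three. If a report then says that a secondary endpoint met its limit, the reader cannot attach a family-wise error rate of 0.025 to that statement.

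The limits themselves are also not visible. For the primary, SAP 7.6 points to a threshold in the protocol, and 60% is printed there. For the secondaries, SAP 7.7 points to guideline principles without naming the guideline. SAP 7.9.5 cites a CLSI guideline for definitions, and SAP 7.13 mentions a CFDA review guideline; 7.7 does not say whether either is meant. No limit for MARD or Consensus A+B appears in either document, and no direction is given for MARD.

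**Working it through.** **1. The plan's own figure.** Neither document states a family-wise error rate or a power for the secondaries. The one design figure is the sample size for the primary (protocol 14.5, SAP 6.2): σ = 0.32, difference 0.72 − 0.60 = 0.12, one-sided 0.025, power 80%.

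- n = σ²(t_α + t_β)² / (difference)², iterated on the t distribution, gives 57.8, so 58. This matches the plan.
- Power at n = 58 from the noncentral t is 0.802.

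The design therefore supports one test at 0.025, that of the primary.

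**2. Family-wise error across the three secondaries.** Inputs: three endpoints (SAP 7.7), one-sided 0.025 each (SAP 6.9), no adjustment (SAP 6.8). Assumptions: every true value lies exactly at its limit, each test keeps its 0.025 level, and an error means at least one false pass.

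- Upper bound under any dependence: 3 × 0.025 = 0.075.
- Independent tests: 1 − 0.975³ = 0.0731.
- Equally correlated normal test statistics, by simulation with 1,000,000 draws. The correlations are assumed, because the documents give none:

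| Correlation | Chance of at least one false pass |
|---|---|
| 0.3 | 0.068 |
| 0.5 | 0.063 |
| 0.8 | 0.049 |
| 0.95 | 0.037 |

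All of these exceed 0.025. A Bonferroni split would need 0.025 / 3 = 0.0083 per test. A fixed sequence after the primary would allow 0.025 at each step.

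**3. Does each test keep its 0.025 level?** For MARD, a subject-level t test is planned, so repeated pairs within a subject are not counted as independent. For the two A+B rates the analysis is on pooled measurements, and SAP 7.7 states no allowance for repeated pairs. As an illustration, a 7-hour session with draws every 15 minutes (protocol 9.2.5 and 9.9.1) gives 7 × 60 / 15 + 1 = 29 pairs per subject. With intraclass correlation ρ, the design effect is 1 + 28ρ, and the actual one-sided level of an interval that ignores clustering is 1 − Φ(1.96 / √(design effect)):

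| Assumed ρ | Design effect | Actual level |
|---|---|---|
| 0.02 | 1.56 | 0.058 |
| 0.05 | 2.40 | 0.103 |
| 0.10 | 3.80 | 0.157 |

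The documents give no ρ for zone A+B. The table shows only that ordering the tests would not by itself secure 0.025 for a) and b).

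**4. Wording of the limit.** The 95% limit in SAP 7.7 agrees with one-sided 0.025 in SAP 6.9 only as one end of a two-sided 95% interval. Read as a one-sided 95% limit, each test would be at 0.05, and the independent family rate would be 1 − 0.95³ = 0.143.

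**The case against.** **The trial's decision is untouched.** Protocol 14.9 uses the primary alone, and its error stays at 0.025. This stands. A reader might infer that a failed primary could be rescued by a secondary, or that the trial's error is 1 − 0.975⁴ = 9.6%. The documents support neither: no secondary success rule is written, and pooling the primary with the secondaries merges a decision that the protocol keeps separate.

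**Each test has a nominal level.** This also stands. It would be too strong to say that the secondaries have no error control at all. If the limits were fixed beforehand in the guideline, each test is nominally at 0.025 and the family rate is bounded. Only joint control is missing.

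**The endpoints overlap.** All three come from the same pairs of primary-sensor and YSI values, and two are zone rates on alternative grids. Independence is therefore unlikely, and 7.3% is close to the ceiling. If all three limits had to be met together there would be no inflation, but the SAP does not state such a rule.

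**The limits may exist elsewhere.** SAP 7.7 does fix them by reference, and whether the guideline contains them cannot be checked here. One related figure is printed: SAP 7.9.3, repeating protocol 14.12.3, says that if a method "has a high percentage (greater than (>) 90%) of its pairs in Zones A and B, then it is considered clinically acceptable". That is a description of the Clarke grid and is not named as the test limit. SAP 7.13 drops two analyses because "there is no requirement in CFDA registration technical review guideline", which suggests that the comparison is meant for a regulator. That is a reason to keep the comparison as a descriptive one. It does not show that a formal test was planned in the protocol.

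**Conclusion.** The point holds as a discrepancy between protocol and SAP with a limited inferential consequence. The SAP turns three estimation-only endpoints into three formal tests without adjustment, without a condition on the primary and without recording the change. Family-wise error across the three is at most 7.5%, 7.3% if independent, and about 6.3% to 3.7% at assumed correlations of 0.5 to 0.95, against 0.025 per test. These figures assume true values at the limits, an at-least-one-pass reading, and a 0.025 level that each test actually keeps. The last assumption is doubtful for the two A+B rates as planned. The success criterion, sample size and power of the primary are not affected, so this is a change that should be made but does not threaten the trial's main conclusion.

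**What to change.** **Preferred.** In SAP 6.9, restrict the one-sided 0.025 test to the primary endpoint. In SAP 7.7, report MARD and the two A+B rates with two-sided 95% confidence intervals, as the protocol says, and label any comparison with guideline limits as descriptive.

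**If formal secondary tests are wanted:**

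- name the guideline and write the three numerical limits into SAP 7.7;
- state the direction of each (upper limit for MARD, lower limit for the A+B rates) and that the limit is one end of a two-sided 95% interval;
- test in a stated fixed order, starting only after the primary has passed and stopping at the first failure;
- use subject-level or cluster-adjusted intervals for a) and b), so that each 0.025 level holds;
- list the move from interval to test in SAP 7.13.

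**Cost.** The preferred option changes SAP wording only. The second also changes how the two A+B intervals are computed. Neither changes the sample size or the primary's power. The downside is that no formal secondary claim can be made if the primary fails (under the preferred option, none is made in any case), which fits the protocol's single pass/fail criterion.

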7.8 Numbers of Reading in the Low and High Ranges

Every effort to safely collect data in the low and high range via the hyperglycemic and hypoglycemic challenge will be made.

The number and percentage of YSI values collected when Sensor readings displayed 'Low' (less than 40 mg/dL) and 'High' (greater than 400 mg/dL) will be provided.

This part of indicators will be summarized by descriptive statistics. The analysis method will be referred to section 7.2.

7.9 Other Descriptive Endpoints

- Data from the home-use portion will be described. Analysis will include but not be limited to: 20% mean agreement rate (± 20 mg/dL (1.1 mmol/L) when Reference BG less than or equal to (\leq) 80 mg/dL (4.4 mmol/L)) for all fingersticks (capillary SMBG) collected, Clarke Error Grid Analysis (EGA), Consensus Error Grid analysis, Absolute Relative Difference (ARD), bias, correlation between Enlite Sensor and fingersticks (capillary SMBG), and Bland-Altman plots. In addition, 20% mean agreement rate (± 20 mg/dL (1.1 mmol/L) when Reference BG less than or equal to (\leq) 80 mg/dL (4.4 mmol/L)) will be described by the subgroups mentioned below: frequent sampling. The number of actual calibrations performed per day by study subjects will be tabulated and presented.
- Similar descriptive subgroup analysis of Enlite Sensor performance with YSI in all devices will be performed.
 - **FST:**
 - Day 1
 - Day 3-4
 - Day 6
- Precision analysis: ARD, bias, and 20% mean agreement rate (± 20 mg/dL (1.1 mmol/L) when Reference BG less than or equal to (\leq) 80 mg/dL (4.4 mmol/L)) will be performed.

This part of indicators will be summarized by descriptive statistics. The analysis method will be referred to section 7.2.

7.9.1 Difference Tables Comparing Sensor and Reference Readings

Number and percentage of paired data points within 10%, 15%, 20%, 30%, 40%, 50%, 60%, 70%, 80%, 90% and 100% of the reference method (YSI for in-clinic portion and meter BG for home-use portion) will be summarized.

Number and percentage of paired data within 10 mg/dL, 15 mg/dL, 20 mg/dL, 30 mg/dL, 40 mg/dL, 50 mg/dL, 60 mg/dL, 70 mg/dL, 80 mg/dL, 90 mg/dL and 100 mg/dL Of the reference method (YSI for in-clinic portion and meter BG for home-use portion) will be summarized.

This part of indicators will be summarized by descriptive statistics. The analysis method will be referred to section 7.2.

7.9.2 Sensor Calibration

Characteristics of Enlite Sensor calibration will be evaluated by:

- Rate of change (less than (<)-4.0 mg/dL/min, -4.0 to -2.5 mg/dL/min, -2.5 to -2.0 mg/dL/min, -2.0 to -1.5 mg/dL/min, -1.5 to -1.0 mg/dL/min, -1.0 to +1.0 mg/dL/min, +1 to +1.5 mg/dL/min, +1.5 to +2.0 mg/dL/min, +2.0 to +2.5 mg/dL/min, +2.5 to +4.0 mg/dL/min, and greater than (>) +4.0 mg/dL/min).

The detailed calculation is as following:

Rate of change for each SG point can be calculated using the SGs within +/- 20 minutes of that SG point. The rate of change is calculated by the formula below:

For each of SGs before SG of interest:

$$(SG_interest - SG_before(i))/time_interval, i=1, 2, 3, 4, \dots\dots$$

For each of SGs after SG of interest:

$$(SG_after(i) - SG_interest)/time_interval, i=1, 2, 3, 4, \dots\dots$$

Then we average all values to get the rate of change and it can be summarized into different categories.

- Rate of change arrows that are displayed to users.

7.9.3 Clarke Error Grid Analysis (EGA) of Paired Sensor and YSI and Reference Values

1) Description

Clarke EGA separates paired observations into five zones of clinical significance. The presence and severity of possible treatment error based on interstitial glucose assay evaluated by the sensor defines the five zones. Zone A represents the absence of treatment error, where the evaluation method and the reference method are within 20% of one another or in which both methods indicate hypoglycemia. Zone B represents cases where the two methods disagree by more than 20%, but do not lead to treatment error. Zones C, D, and E represent increasingly large and potentially harmful discrepancies between the evaluation and the reference method. If the method under evaluation has a high percentage (greater than (>) 90%) of its pairs in Zones A and B, then it is considered clinically acceptable [Clarke et al, 1987].

2) Statistical analysis

Summary statistics (N, %) for each of the zones, as well as combined Zones A and B, will be calculated.

In order to evaluate differing levels of accuracy at various YSI defined glucose levels, the number and percentage of paired observations falling into Zones A, B, A+B, C, D, and E will be provide form YSI glucose ranges of 40-80 mg/dL, greater than (>) 80-120 mg/dL, greater than (>)120-240 mg/dL, and greater than (>) 240 mg/dL.

All analysis performed using the Clarke Error Grid comparing the paired sensor and YSI reference glucose values will be duplicated using the Consensus Error Grid [Parkes et al, 2000].

7.9.4 Precision Analysis

Precision analysis will be performed for the two sensors worn by the same subject in the same location. This part of indicators will be summarized by descriptive statistics. The analysis method will be referred to section 7.2.

7.9.5 Other Accuracy Analyses

The ARD, the absolute differences between the sensor and YSI relative to the YSI reference will be calculated for each day separately. Summary statistics will include its mean, standard deviation, min, median, and max.

The mean numerical bias, which is the difference between the sensor and YSI values, will be calculated for each day. Summary statistics will include its mean, standard deviation, min, median, and max.

Bland-Altman plots, with 95% CI, will be provided for each of the 3 study days. The paired differences between the sensor and YSI rating will be plotted against the X-axis reference of mean YSI and sensor values.

Descriptive subgroup analysis of Enlite Sensor performance (20% mean agreement rate (± 20 mg/dL (1.1 mmol/L) when Reference BG less than or equal to (\leq) 80 mg/dL (4.4 mmol/L))) will be performed in the following cohorts:

- **FST:**
 - Day 1
 - Day 3-4
 - Day 6

All analysis follow the definitions provided in: Performance Metrics for Continuous Interstitial Glucose Monitoring: Approved Guideline, CLSI POCT05-A [Klonoff et al. 2008].

This part of indicators will be summarized by descriptive statistics. The analysis method will be referred to section 7.1.

7.10 Safety Evaluation

For Safety analysis, no formal hypothesis testing will be performed. Descriptive analytics will be used to summarize safety events. Safety events which will be characterized include:

- Skin assessment of Enlite Sensor insertion sites
- All adverse events (AEs) to include but not limited to:
 - Device Related AE
 - Procedure Related AE
 - Serious Adverse Event (SAE)
 - Serious Adverse Device Effects (SADE)
 - UADE

- Severe Hypoglycemia
- Diabetic Ketoacidosis (DKA)

7.11 Device Deficiencies and Subject Feedback

Descriptive summary will be used to characterize device deficiencies. Descriptive summary will be used to characterize study questionnaire results. The questionnaire will use a Likert scale rating to assess their Enlite Sensor experience.

7.12 Health Outcomes Analyses

Descriptive summary will be used to characterize data from questionnaires that are given to subjects to record feedback.

7.13 Changes to Planned Analysis

1. Analysis result of Continuous Error Grid will not be provided in statistical analysis report as there is no requirement in CFDA registration technical review guideline.
2. Evaluation of “First calibration SMBG value ranges (40 - 70 mg/dL, 70 – 180 mg/dL and 180 - 400 mg/dL): the numerical Sensor Glucose Value (SGV) accuracy will be evaluated against YSI stratified by the first calibration SMBG value up to the second calibration SMBG.” will not be provided in the analysis report as there is no requirement in CFDA registration technical review guideline.

8. Validation Requirements

Level I or Level II validation are required for analysis output. Level I requires that the peer reviewer independently programs output and then compares the output with that generated by the original Statistical Programmer. Level II requires that the peer reviewer reviews the code; where appropriate, performs manual calculations or simple programming checks to verify the output.

9. Mock Tables, Listings and Figures

See SAP appendix tables, listings and figures.
